9.2 Efficacy Assessments

9.2.1 Serum Bile Acids

Blood samples for analysis of fasting serum bile acids will be drawn at all study visits from Visit 1 (Visit S-1 for Cohort 2) through Visit 12. Patients will fast (only water intake is permissible) for at least 4 hours prior to the collection of samples for serum bile acids. Exceptions can be made for infants, less than 12 months of age, if unable to fast for the full 4 hours. For any visit at which a bile acid sample result is unreportable, an additional unscheduled visit for a repeat sample collection may be scheduled. Samples will be handled and transported to a central laboratory per instructions in the laboratory manual.

9.2.2 Itching and Sleep Score

Itching, observed scratching, and sleep disturbance will be assessed twice each day via eDiary. Patient/caregivers will be instructed to fill in the eDiary every morning and evening for the first 24 weeks and the last 21 days before all the remaining visits to the clinic. There will be no interruption between Visits 11 and 12. Patients and/or caregivers will be instructed to complete the eDiary in the morning after the patient wakes and in the evening just before the patient goes to sleep.

The eDiary includes Albireo ObsRO and PRO items. Patients <8 years of age will not be asked to complete the Albireo PRO items; only the Albireo ObsRO will be completed by caregivers of patients in this age group. Older patients, ≥ 8 years of age, will complete the Albireo PRO items and the caregiver will complete the Albireo ObsRO items. The Albireo PRO items assess severity of itch, aspects of sleep disturbance (morning diary only), and tiredness. For patients 8 to 12 years of age, the caregiver will read the Albireo PRO items along with the child and record the child's response. A guide will be provided to the caregivers that provides standardized explanations of the Albireo PRO items, in case the patient is confused or requires clarification about the meaning of a question. The Albireo ObsRO items assess severity of observed scratching, aspects of observed sleep disturbance (morning diary only), and observed signs of tiredness (evening diary only). The Albireo ObsRO and PRO scratching and itch severity items use 0 to 4 response scales, where each response is distinguished by a unique facial expression, verbal anchor, number, and color code ([Appendix 2](#)).

A daily score AM and PM for the Albireo ObsRO scratching item will be averaged from the 2 ratings for each day. A daily score will be considered missing if both of the daily assessments are missing. A weekly score will be calculated by averaging the daily scratching scores. A weekly score will be considered missing if ≥ 4 out of 7 days a week of data are missing. For AM and PM baseline, a 14-day daily score of AM and PM prior to the first dose of study medication will be averaged as the baseline score.

For AM baseline, a 14-day AM score prior to the first dose of study medication will be averaged as the baseline AM score. The same approach will be used for PM baseline and to calculate a patient-reported itch severity score.

9.2.3 Growth

Growth (height and weight) will be measured by the standardized assessments outlined in the US FDA guidance document, *Orally Inhaled and Intranasal Corticosteroids: Evaluation of the Effects on Growth in Children* (March 2007). Height and length (velocity) will be measured using a certified stadiometer and weight (Z-score) using a certified weight scale.

Mid-arm circumference (3 repeat measurements) will be collected at the study site.

Study sites will be trained on using a standardized approach when measuring height with a stadiometer and additional detailed instructions will be provided in study documents.

BMI will be calculated by weight (kg) / height (m)². Change will be defined as linear growth deficit (weight and BMI for age) compared to a standard growth curve.

9.2.4 Biomarker Samples

Blood samples for p-C4 and autotaxin will be drawn at Visits 1, 2, 5, 8, and 11 (p-C4 and autotaxin will only be drawn for patients with body weight >10 kg). Samples will be treated and transported to a central laboratory per instructions in the laboratory manual.

9.2.5 Change of Antipruritic Medication

Any change of antipruritic medication must be noted in the eCRF.

9.2.6 Quality of Life Questionnaire (PedsQL)

Caregivers and, if applicable, patients will be asked to fill out a QoL questionnaire (PedsQL) at Visits 1, 5, 8, and 11. Details of the questions included on the questionnaire can be found in [Appendix 4](#).

9.2.7 PELD/MELD Score

The PELD score will be calculated for children up to 12 years of age. For patients 13 years or older, the MELD score will be calculated.

PELD Score = $4.80 * \ln(\text{total bilirubin}) + 18.57 * \ln(\text{INR}) - 6.87 * \ln(\text{albumin}) + 4.36$ (if patient <1 year: scores for patients listed for liver transplantation before the patient's first birthday)

continue to include the value assigned for age (<1 year) until the patient reaches the age of 24 months) + 6.67 (if patient has growth failure [<-2 SD])

Laboratory values less than 1.0 will be set to 1.0 for the calculation of the PELD score.

MELD Score = $9.57 * \ln(\text{creatinine}) + 3.78 * \ln(\text{total bilirubin}) + 11.2 * \ln(\text{INR}) + 6.43$

Laboratory values less than 1.0 will be set to 1.0 and serum creatinine values greater than 4.0 mg/dL (equivalent to 353.6 $\mu\text{mol/L}$) will be set to 4.0 for calculation of the MELD score.

If a patient goes from 11 years of age to 12 between the beginning and end of study, both PELD and MELD scores will be calculated at the first visit after the 12th birthday and move to MELD score. The results should be displayed in one summary table.

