7.2.1 Inclusion Criteria

Cohort 1:

1. Completion of the 24-week Treatment Period of Study A4250-005 or withdrawn from Study A4250-005 due to patient/caregiver judgment of intolerable symptoms after completing at least 12 weeks of treatment. Patients who withdraw from A4250-005 due to a study drug related AE will not be eligible.
2. Signed informed consent and assent as appropriate. Patients who turn 18 years of age (or legal age per country) during the study will be required to re-consent to remain on the study.
3. Patients expected to have a consistent caregiver for the duration of the study.
4. Caregivers (and age-appropriate patients) must be willing and able to use an eDiary device as required by the study.

Cohort 2:

1. A male or female patient of any age, with a clinical diagnosis of PFIC, including episodic forms (i.e., BRIC), and with a body weight ≥ 5 kg at Visit S-1.
2. Patient must have clinical genetic confirmation of PFIC.
3. Patients with PFIC, excluding BRIC, must have elevated serum bile acid concentration, specifically measured to be ≥ 100 $\mu\text{mol/L}$, taken as the average of 2 samples at least 7 days apart (Visits S-1 and S-2) prior to the Screening/Inclusion Visit (Visit 1).

4. Patients with PFIC, excluding BRIC, must have history of significant pruritus and a caregiver-reported observed scratching or patient-reported itching (for patients >18 with no caregiver-reported observed scratching) in the eDiary average of ≥ 2 (on 0 to 4 scale) in the 2 weeks prior to the Screening/Inclusion Visit (Visit 1).
5. Patients with episodic forms of PFIC (i.e., BRIC) must have an emerging flare characterized by clinically significant pruritus and elevated serum bile acid levels/cholestasis as judged by the investigator.
6. Patient and/or legal guardian must sign informed consent (and assent) as appropriate. Patients who turn 18 years of age (or legal age per country) during the study will be required to re-consent in order to remain in the study.
7. Age appropriate patients are expected to have a consistent caregiver for the duration of the study.
8. Caregivers and age-appropriate patients (≥ 8 years of age, if able) must be willing and able to use an eDiary device as required by the study.

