- Change in pediatric end-stage liver disease (PELD)/model for end-stage liver disease (MELD) score from baseline to Week 72
- Change in use of antipruritic medication at Weeks 24, 48, and 72

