11.2.2 Methods of Statistical Analyses

11.2.2.1 General Principles

Descriptive statistics will mainly be used in this open-label extension study. Patients with BRIC will be presented separately in efficacy assessments. All statistical analyses will be performed using SAS version 9.3 or higher.

Baseline 1 will be defined as the last value prior to treatment start in Study A4250-005 for Cohort 1 patients.

Baseline 2 will be defined as the last value prior to treatment start in Study A4250-008 for all patients. Baseline 2 will be used in all analyses unless otherwise specified.

Descriptive statistics will be summarized for Cohort 1, Cohort 2 excluding BRIC, Cohort 2 BRIC, and combined Cohort 1 + Cohort 2 excluding BRIC. Within Cohort 1, the following subgroups will be presented: ‘A4250 40 µg/kg/day (-005) to 120 µg/kg/day (-008)’, ‘A4250 120 µg/kg/day (-005) to 120 µg/kg/day (-008)’, ‘A4250 40 µg/kg/day (-005) and 120 µg/kg/day (-005) to 120 µg/kg/day (-008)’, and ‘placebo (-005) to 120 µg/kg/day (-008)’. Within Cohort 2 excluding BRIC, 3 subgroups (‘40 µg/kg/day’, ‘40 µg/kg/day to 120 µg/kg/day’, and ‘120 µg/kg/day’) will be presented. Cohort 1 Placebo to A4250 120 µg/kg/day will also be combined with Cohort 2 excluding BRIC for presentations.

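### The under-1-year PELD term lapses before Week 72, so infants not listed for transplantation by their first birthday show a 4.36-point fall with unchanged laboratory values and growth status

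*Protocol*

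**What the plan says.** Protocol section 9.2.7 defines PELD as a weighted sum of the logarithms of total bilirubin, INR and albumin. It adds 4.36 points for a patient under 1 year and 6.67 for growth failure. The age term has one extension: "scores for patients listed for liver transplantation before the" first birthday "continue to include the value assigned for age (<1 year) until the patient reaches the age of 24 months". Laboratory values below 1.0 are set to 1.0. The section also gives a transition rule for patients who turn 12 during the study and asks for one summary table. It gives no rule for patients who turn 1.

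Section 9.1.2 lists as a secondary endpoint: "Change in pediatric end-stage liver disease (PELD)/model for end-stage liver disease (MELD) score from baseline to Week 72". Section 11.2.2.6 analyses continuous secondary variables descriptively, as visit values and as change from baseline. Section 11.2.2.1 sets the reference point: "Baseline 2 will be defined as the last value prior to treatment start in Study A4250-008 for all patients". Infants can enter Cohort 2, which under section 7.2.1 admits "A male or female patient of any age" from 5 kg body weight. Section 9.2.1 makes a fasting exception for infants under 12 months.

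**The concern.** The score contains a component that switches off with age, and follow-up is longer than the age band that switches it on. For an infant, a fall in PELD between baseline and Week 72 therefore mixes any change in the liver tests with the passing of a birthday. The fall always has the sign of an improvement.

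Nothing in the design removes it. The study is single-arm. The exploratory comparison with placebo patients of Study A4250-005 (section 11.2.2.5) covers pruritus and serum bile acids only, and the comparison with the NAPPED cohort (section 11.2.2.6) covers surgical events and death. What is at stake is the interpretation of one secondary endpoint in the youngest patients.

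**Working it through.** **Inputs.** Age term 4.36 and coefficients 4.80 (bilirubin), 18.57 (INR) and 6.87 (albumin), section 9.2.7. Week 72 at Day 504 ±7 and Week 70 at Day 490 ±7, Table 1. One month is taken as 30.4375 days. The number of infants is not stated.

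**1. The visit day.** 72 × 7 = 504, which reproduces Table 1.

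**2. Youngest possible age at scoring.** A patient aged 0 days on Day 1 is 497 - 1 = 496 days old at the earliest Week 72 visit: 496 / 30.4375 = 16.3 months. Table 1 shows no INR draw at Visit 11, so the Week 70 INR may be used. If the score were dated at the earliest Week 70 visit (Day 483), the minimum age is 482 / 30.4375 = 15.8 months. Either way the first birthday has passed.

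**3. Listed infants.** The term lasts to 24 months. At Day 504, 503 / 30.4375 = 16.5 months have elapsed, so a listed infant keeps the term only if younger than 24 - 16.5 = about 7.5 months at entry (7.2 to 7.7 across the visit window). Older listed infants lose it too.

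**4. Effect on one patient.** Take bilirubin 6, INR 1.2, albumin 3.5 and no growth failure at both visits (illustrative values):

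- Laboratory part: 4.80 × ln 6 + 18.57 × ln 1.2 - 6.87 × ln 3.5 = 8.60 + 3.39 - 8.61 = 3.38
- Baseline: 3.38 + 4.36 = 7.74
- Week 72: 3.38
- Change: -4.36

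The result does not depend on the laboratory values chosen, because they cancel. With the term held at its baseline value, or left out of both scores, the change is 0.

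**5. What 4.36 points is worth.**

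- Bilirubin: exp(-4.36 / 4.80) = 0.403, a 60% fall. Because values stop at 1.0, this is reachable only from 1 / 0.403 = about 2.5 or higher (mg/dL assumed; section 9.2.7 does not state the bilirubin unit).
- INR: exp(-4.36 / 18.57) = 0.791, a 21% fall, reachable only from 1 / 0.791 = about 1.26 or higher. Cohort 2 excludes INR above 1.4 unless it is at or below 1.4 at resampling, so the range in which INR alone could do this is narrow.

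**6. Effect on a group mean.** Shift = -4.36 × share of PELD-scored patients who lose the term. The shares are assumed:

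| Share | Shift (points) |
|---|---|
| 5% | -0.22 |
| 10% | -0.44 |
| 15% | -0.65 |
| 20% | -0.87 |
| 25% | -1.09 |

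**The case against.** Four arguments tell against giving this much weight.

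- **No decision rests on it.** Section 11.1 states that there is no formal hypothesis testing. PELD/MELD change is one item in a long secondary list and has no threshold. This stands, and it lowers the severity.
- **The components are visible.** Section 9.1.3 reports changes in total bilirubin, INR and albumin in their own right. A PELD fall with flat components could be noticed. This also stands, but it leaves the summary of the composite score wrong for these patients.
- **Infants may be few.** Cohort 1 reaches baseline only after Study A4250-005. A 24-week completer still under 12 months must have entered that study before 12 - 168 / 30.4375 = about 6.5 months of age, so Cohort 1 may be almost unaffected. A high overall share is hard to reach: 30% of about 120 patients is 36, which would have to come almost entirely from the 60 in Cohort 2. This stands.
- **The SAP can settle it.** The derivation needs completing anyway, since Table 1 has no INR draw at Visit 1 or Visit 11. But section 9.2.7 fixes the formula and already handles one age transition. An SAP that held the term constant would depart from the protocol as written.

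A reader might infer that every infant loses the term. The text does not support that: a listed infant younger than about 7.5 months at entry keeps it at Week 72, including one listed after baseline but before the first birthday, and an infant withdrawn early may be scored while still under 1 year. A reader might also infer that the term is unrelated to liver function. The protocol does not say what it represents, and the argument does not need it.

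**Conclusion.** The point holds, as a minor one. By the protocol's own formula and visit schedule, a patient under 1 year at baseline who is scored at Week 72 shows -4.36 points with unchanged laboratory values and growth status if not listed by the first birthday, or if listed and older than about 7.5 months at entry. This is a fixed offset added to whatever real change occurs: an infant whose laboratory part worsens by more than 4.36 points would still show a rise, though too small a one.

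The per-patient figure needs no assumption. The group figure does: about -0.2 points for each 5% of PELD-scored patients affected, with the true share unknown. The documents do not support a claim that the overall PELD/MELD result is materially distorted, or that any conclusion of the trial would change.

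**What to change.** Add a rule to section 9.2.7: for change from baseline, the under-1-year term is held at its baseline value at all visits, or omitted at all visits. The change score then moves only with bilirubin, INR, albumin and growth failure, and transplant listing no longer affects it. Report the conventional PELD score alongside.

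The cost is one sentence and one extra derivation, with no new data. The drawback is a change score that differs from conventional PELD; if the term is held, a child approaching or past 2 years still carries an under-1-year value. Omitting the term at all visits avoids that.

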9.2.8 Fibroscan®

Where available, Fibroscan® will be performed as per institution standard practice at Visits 1, 5, 8, and 11.

9.2.9 Markers of Fibrosis

APRI score and Fib-4 score will be calculated at Visits 1, 3, 5, 8, and 11.

APRI = $[(\text{AST in U/L}) / (\text{AST upper limit of normal [ULN] in U/L})] \times 100 / (\text{Platelets in } 10^9/\text{L})$

Fibrosis 4 Score = $(\text{Age} * \text{AST in U/L}) / (\text{Platelets in } 10^9/\text{L} * \sqrt{\text{ALT in U/L}})$

9.2.10 Liver Biopsy

If a liver biopsy is performed according to the local regulations or standard of care at any time during A4250-008, the biopsy results should be recorded in the eCRF. If the patient has liver biopsy results collected in study A4250-005 or prior to Week 24 in study A4250-008, the patient will be asked to consent to a follow up liver biopsy, if allowed per local regulations, at Visit 11 unless 2 prior liver biopsy results have been collected with at least 1 year between biopsies. Liver biopsies will not be performed in Spain.

9.2.11 Global Impression of Change and Global Impression of Symptom Measures

Patients, caregivers, and clinicians will complete the PGIC and the PGIS measures at Visits 1, 2, 3, 5, 8, and 11 ([Appendix 3](#)).

The PGIC items assess change in itch (patient version), scratching (caregiver and clinician versions), and sleep (all versions) since starting the study drug. The PGIS items assess itch (patient version), scratching (caregiver and clinician versions), and sleep (all versions) in the past week. Caregivers and clinicians will complete the PGIC and PGIS for all patients; those patients ≥ 8 years of age will complete the patient version.

10 ASSESSMENT OF SAFETY

The timing and frequency of safety assessments are described in [Section 7.1.2](#) and [Section 7.1.3](#).

The primary safety analysis for this study will include the incidence of total treatment-emergent adverse events (TEAE) and TEAEs categorized by causality, severity, and seriousness assessments.

Trends in safety will also be evaluated for the following assessments:

- Physical examinations
- Concomitant medications
- Vital signs
- Laboratory test results (including clinical chemistry, hematology, urinalysis, AFP, vitamins A, E, and 25-hydroxy vitamin D, and INR)
- Abdominal ultrasound
- Discontinuations due to AEs

10.1 Adverse Events

10.1.1 Definitions and Investigator Assessments

An AE is defined as any untoward medical occurrence in an enrolled patient regardless of causal relationship with study drug. An AE can therefore be any clinically significant unfavorable and unintended sign, symptom, or disease that occurs once a patient is enrolled (ICF is signed) in the study until the patient is discharged from the study, whether or not related to the study drug.

10.1.1.1 Clinical Significance

Clinical significance is defined as any abnormal finding that results in further clinical investigation(s), treatment(s), or the diagnosis of new condition. Patient-reported events and protocol-mandated laboratory values, vital signs, and physical examination findings can be considered clinically significant (i.e., an AE) if there is a deterioration as compared to baseline. Examples of clinically significant worsening from baseline could include, but is not limited to, events causing withdrawal from the study and events requiring medical intervention outside of the study causing apparent clinical manifestations, or judged relevant by the investigator.

10.1.1.2 Serious Adverse Events

Serious criteria are applied by the investigator to each AE as specifically defined below. These criteria are used to determine whether an AE is serious or non-serious. The assessment is made independently of severity assessment ([Section 10.1.1.3](#)). For example, the development of a

severe rash that occurs after signing of informed consent may not meet serious criteria as defined below and therefore would be considered a severe, non-serious AE.

Any AE that meets any 1 of the following 6 criteria is considered an SAE:

- The outcome of the AE is **death**
- The AE is immediately **life-threatening**. Life-threatening means that the patient is, in the opinion of the investigator, at immediate risk of death from the reaction as it occurred. This does not include an AE that, if more severe, might have caused death
- The AE results in persistent or significant **disability/incapacity**. Disability means a substantial disruption of a person's ability to conduct normal life functions
- The AE requires or prolongs **hospitalization**
- The AE results in a **congenital anomaly/birth defect**
- **The AE is an important medical event.** Important medical events may meet serious criteria should the investigator assess that they may significantly jeopardize the patient, represent a significant hazard, or requires medical/surgical intervention to prevent one of the outcomes listed above. Examples of potential SAEs based on this criterium include, but are not limited to, allergic bronchospasm requiring intensive treatment in an emergency room or at home, blood dyscrasias or convulsions even if they do not result in inpatient hospitalization, or the development of drug dependency and drug abuse.

10.1.1.3 Severity Assessment

Severity assessments are based on the intensity of the event in relation to expectation. The investigator will assess the intensity of AEs based on the following definitions:

- Mild (awareness of sign or symptom, but easily tolerated)
- Moderate (discomfort sufficient to cause interference with normal activities)
- Severe (incapacitating, with inability to perform normal activities)

Severity is a measure of intensity where seriousness is defined by the criteria outlined in **Section 10.1.1.2**. An AE of severe intensity need not necessarily be considered serious. For example, nausea that persists for several hours may be considered severe nausea, but not meet serious criteria, and therefore would be assessed as a severe AE but not an SAE.

10.1.1.4 Causality Assessment

The investigator determines the causality of all AEs to the study drug using medical judgment and considering all relevant factors such as (but not limited to) the underlying study indication, coexisting disease, concomitant medication, relevant history, pattern of the AE, temporal relationship to the study drug, and de-challenge or re-challenge. The causality assessment of the AE/SAE is to be made as follows.

Related to study drug (possibly, probably, or definitely related)

Based on medical judgment, there is at least a reasonable possibility that the study drug caused the event; one or more of the following criteria apply:

- The event follows a reasonable temporal sequence from administration of study drug
- The event could not be reasonably attributed to the known characteristics of the patient's clinical state, environmental or toxic factors, or other modes of therapy administered to the patient
- The event follows a known pattern of response to study drug
- The event disappears or decreases on cessation or reduction in dose of the study drug. (It should be noted that in some situations an AE will not disappear or decrease in intensity upon discontinuation of study drug despite other clear indications of relatedness)
- The event reappears or worsens when the study drug is re-administered

Unrelated to study drug (unlikely or unrelated)

Based on medical judgment there is no reasonable possibility that the study drug caused the event; one or more of the following criteria apply:

- The event does not follow a reasonable temporal sequence from administration of study drug
- The event could be reasonably attributed to the known characteristics of the patient's clinical state, concurrent illness, environment or toxic factors, or other modes of therapy administered to the patient
- The event does not follow a known pattern of response to study drug
- The event does not disappear or decrease on cessation or reduction in dose of the study drug, and it does not reappear or worsen when the study drug is re-administered

